3. STUDY DESIGN

3.1 Overview:

This is an exploratory, single center, observer masked, active control, 1:1 randomized clinical trial. The goal is to compare the effectiveness of Study Device (Cutimed® Sorbact® wound contact layer) to an active control (silver contact layer Acticoat®). Both devices are already approved and indicated for treatment of wounds. Standard care selected for use in this trial includes sharp debridement and compression with Jobst Comprifore® 4 layer compression system.

The study consists of three phases: two weeks screening phase (phase-1), up to four weeks treatment phase (phase-2), and two weeks follow up phase (phase-3).

In the screening phase i.e. phase-1, the Investigators will choose Study Ulcer, make baseline measurements and assessments and verify inclusion and exclusion criteria are met. Standard care will be applied without use of Study Device or active control.

The treatment phase i.e. phase-2 may last up to four weeks (if healing did not occur prior) and includes application of study dressings as well as application of standard care and measurements of primary and secondary outcomes. This will be achieved by tissue collection procedures conducted at visits T0, T2, and T3. [name] and her research team will conduct the molecular microbiology and standard microbiology assessments of the specimens collected in this study. Gene expression (by qPCR) and standard microbiology will be utilized to characterize the mechanisms through which Cutimed® Sorbact® changes the bacterial load and promotes healing of chronic venous leg ulcers. Understanding the mechanism through which Cutimed® Sorbact® stimulates healing in patients may promote, improve and expand its clinical use.

In the two weeks follow up phase i.e. phase-3 subjects will return for one visit and secondary outcomes will be assessed and standard care provided. The subjects will then be discharged from the study and return to their wound care provider for further management as indicated.

3.2 Study outcomes:

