3.2.2 Secondary outcomes

Secondary outcomes will include:

Microbiological outcomes: bacterial silver resistance characterization on molecular and phenotypic level over time (see appendix A for molecular microbiology protocol).

Clinical wound outcomes: healing rate and percent reduction in area over 6 weeks will be calculated by measuring wound area at each visit and dividing the area change by 6 to calculate average wound healing rate in cm^2/week and the average percent reduction for each study arm.

Complete healing at 6 weeks – the proportion of subjects in each study arm in which the study ulcer achieved complete healing at visit F1.

Pain related outcomes: pain assessments will be collected at every visit using visual analog scale (VAS) and time from visit T0 to clinically meaningful decrease in pain (i.e. 33% reduction from baseline) [21] will be calculated. Additionally, time to first indication of no pain will be calculated (i.e. VAS < 5mm)

Quality of life measurements: the EQ-5D-5L [22] and the Wound Quality of Life (WQoL) [23, 24] instruments will be used and assessments take place at visits T0, T4 and F1.

Safety outcomes: adverse events will be recorded at every visit and type and frequency logged and compared between arms.

4. Study population

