4.4 Definition of study completion

A subject will be considered as completed the study if:

1. Subject healed during the treatment or follow up phase and completed all visits in the follow up phase.
2. Subject did not heal and completed all visits in the treatment and follow up phase.
3. Subject healed and then wound recurred and completed the follow up phase.

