5.7 Quality of life assessments

The EQ-5D-5L and the WQoL instruments will be used and assessments take place at visits T1, F1 and F2. The EQ-5D-5L consists of 2 pages – the EQ-5D-5L descriptive system (page 2) and the EQ Visual Analogue scale (EQ VAS) (page 3). The descriptive system is comprised 5 dimensions: mobility, self-care, usual activities, pain/discomfort, anxiety/depression. Each dimension has 5 levels: no problems, slight problems, moderate problems, severe problems, and extreme problems. The subjects will be asked to indicate his/her health state by checking in the box against the most appropriate statement in each of the 5 dimensions. The EQ VAS records the respondent's self-rated health on a 20 cm vertical, visual analogue scale with endpoints labelled 'the best health you can imagine' and 'the worst health you can imagine'. This information can be used as a quantitative

measure of health as judged by the individual respondents. The instruments and detailed instructions are presented in appendix 9.8.

The WQoL instrument was developed specifically to address health related quality of life outcomes in people with wounds [24]. The WQoL is a short questionnaire measuring health-related quality of life (HRQoL) in chronic wounds and is composed of seventeen items attributed to three subscales on everyday life, body, and psyche.

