5.21 Instructions for follow up care

Once subjects are identified as healed, they will move into the follow up phase. Subjects who completed the treatment phase (regardless of healing status) will be moved to the follow up stage as well. While in the follow up phase, subjects will be returned to the care provider who referred them to the study and follow up care will consist of appropriate compression therapy, wound care (if needed) and other medically indicated treatments as determined by the PI.

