8.5 Study duration and premature termination

8.5.1 Each subject is enrolled in the study for eight weeks. It is anticipated that the study will be complete (i.e. last subject completed all eight weeks) within one year of first subject recruitment.

8.5.2 It is the intention of all parties to carry out the study to completion. However, if the PI, Sponsor, IRB or any other regulatory authority are made aware of any circumstances that suggest study subjects are at risk if the study continues, the PI or Sponsor, may decide on early termination of the study. Early termination decision will be taken in consultation between both PI and Sponsor.

CONFIDENTIAL

9 Appendices:

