9.7 Appendix G

Wound-QoL questionnaire on quality of life with chronic wounds

With the following questions, we aim to find out how your chronic wound(s) affect(s) your quality of life.

Please tick one box per line!

In the last seven days...

		not at all	a little	moderately	quite a lot	very much
1	...my wound hurt					
2	...my wound had a bad smell					
3	...there was a disturbing discharge from the wound					
4	...the wound has affected my sleep					
5	...the treatment of the wound has been a burden to me					
6	...the wound has made me unhappy					
7	...I have felt frustrated because the wound is taking so long to heal					
8	...I have worried about my wound					
9	...I have been afraid of the wound getting worse or of new wounds appearing					
10	...I have been afraid of knocking the wound					
11	...I have had trouble moving about because of the wound					
12	...climbing stairs has been difficult because of the wound					
13	...I have had trouble with day-to-day activities because of the wound					
14	...the wound has limited my leisure activities					
15	...the wound has forced me to limit my activities with others					
16	...I have felt dependent on help from others because of the wound					
17	...the wound has been a financial burden to me					

"Wound-QoL" questionnaire on Health-related Quality of Life in Chronic Wounds • Augustin et al. 2014;
Blome et al. 2014

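### Subjects who heal at T1–T3 are not required to attend T4, so the quality-of-life score planned for that visit is missing because of their outcome

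*Combined protocol and SAP*

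**What the plan says.** **Quality-of-life visits.** Section 3.2.2 states that the EQ-5D-5L and Wound-QoL "instruments will be used and assessments take place at visits T0, T4 and F1". The QOL row of Table 1 marks the same three visits, with T0 after randomisation. Section 5.7, which describes the procedure, disagrees: the "instruments will be used and assessments take place at visits T1, F1 and F2". That list has no T4, and Table 1 has no F2.

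**Path of a subject who heals early.** Section 3.1 lets the treatment phase run for up to four weeks and ends it sooner if the ulcer heals. Section 5.21 adds: "Once subjects are identified as healed, they will move into the follow up phase". In that phase, according to 3.1, "subjects will return for one visit and secondary outcomes will be assessed". Section 4.4 counts as complete a case described as "Subject healed during the treatment or follow up phase and completed all visits in the follow up phase". Treatment-phase visits are required only of subjects who did not heal.

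**Analysis.** Section 7 analyses quality of life by methods similar to those for the primary endpoint, which are a t-test on change from baseline and a repeated measures regression. It names no visit or contrast for quality of life. On missing data it promises to describe amount, pattern and randomness, but gives no rule for handling them.

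**The concern.** T4 is one of only two post-baseline quality-of-life visits in 3.2.2. On the path described, a subject whose ulcer closes at T1, T2 or T3 has F1 as the only visit left, and no questionnaire is scheduled at the visit where healing is found. The missing T4 score is therefore produced by the outcome and by following the plan.

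Any effect estimate taken at T4 would then refer only to subjects still unhealed after T3. If part of a dressing's benefit to quality of life comes through closing the ulcer, that part is absent at T4. Section 7 says that the pilot exists to generate effect estimates for sizing later studies, so an estimate from a subset selected by outcome could be carried forward. A score not collected in week 4 cannot be recovered later.

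**Working it through.** **Plan's own figures.** There is no quality-of-life effect, healing rate or power figure to reproduce. The one sample-size figure that can be checked is the maximum enrolment of 35 for 30 completers with 15% dropout (4.1): 30 × 1.15 = 34.5, rounded up to 35; 30 / 0.85 = 35.3, rounded up to 36. The point does not turn on this, nor on the 45 subjects given in the Executive Summary.

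**Inputs**
- n = 15 completers per arm (4.1).
- p = share healed by T3. Not in the documents; assumed 5–30%, with 40% in one arm as an extreme.
- g = quality-of-life advantage of healed over unhealed subjects, in SD. Not in the documents; assumed 0.5–1.0.
- Simple model: apart from healing, the arms do not differ.

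**T4 forms missing because of healing.** Expected number = 30p; chance of at least one = 1 − (1 − p)^30.

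| p | Missing of 30 | Left per arm | Chance of at least one |
|---|---|---|---|
| 5% | 1.5 | 14.25 | 79% |
| 10% | 3 | 13.5 | 96% |
| 20% | 6 | 12 | 99.9% |
| 30% | 9 | 10.5 | >99.9% |

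**Mean gain within an arm.** In this model the all-subject mean exceeds the mean of T4 attenders by p × g. At p = 20% that is 0.20 × 0.5 = 0.10 SD to 0.20 × 1.0 = 0.20 SD.

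**Difference between arms.** The T4 comparison loses (pA − pB) × g:
- 20% vs 10%: 0.10 × 0.5 = 0.05 SD to 0.10 × 1.0 = 0.10 SD.
- 30% vs 10%: 0.20 × 0.5 = 0.10 SD to 0.20 × 1.0 = 0.20 SD.
- Equal healing: 0 at any g.

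A simulation of 30% vs 10% with g = 1 SD (15 per arm, 20,000 runs) gave a mean arm difference of 0.202 SD in all subjects and 0.002 SD among T4 attenders. The healing-mediated difference disappears and is not reversed.

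**Precision.** SE ratio = √{[1/(15(1 − pA)) + 1/(15(1 − pB))] / (2/15)}:
- 20% / 20%: √(1/0.8) = 1.12.
- 30% / 10%: √[(1/0.7 + 1/0.9)/2] = 1.13.
- 40% / 20%: √[(1/0.6 + 1/0.8)/2] = 1.21.

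The difference detectable with 80% power (two-sided 5% assumed, normal approximation) is (1.96 + 0.84) × √(2/n): 1.02 SD at 15 per arm and 1.14 SD at 12.

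**Scale.** The SE at 15 per arm is √(2/15) = 0.37 SD, so a shift of 0.10–0.20 SD is about 0.27–0.55 of one standard error.

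**The case against.** **No T4 contrast is planned.** The primary t-test compares the last tissue visit with baseline. The closest quality-of-life analogue is F1 against T0, and early healers are due a score at both. A repeated measures model would also use those scores. This stands. A reader might infer that early healers drop out of the quality-of-life analysis, or out of a specified T0–T4 test; the documents support neither. What remains is that T4 is a planned assessment, and a model estimate there would rest on a missing-at-random assumption that the plan does not state.

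**Healed subjects may attend T4 anyway.** Section 8.5.1 says "Each subject is enrolled in the study for eight weeks", and Table 1 places stocking fitting, which 5.20 ties to healing, at T4 and F1. Both are compatible with attendance, so it is too strong to say that healed subjects never have a T4 visit. But neither says that they attend, and stocking fitting at T4 equally suits a subject first found healed there. If attendance is intended, a sentence saying so is still needed.

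**Early healing may be uncommon.** Exclusion criterion 2 removes ulcers whose area changed by more than 30% during screening. Taking that period as two weeks, the fastest eligible linear shrinkage is 15% of the initial area per week, which leaves 70% at T0 and 70 − 3 × 15 = 25% at T3. Closure by T3 then needs acceleration after randomisation. The Background figure of up to 50% not healing carries no time frame and does not support a week-3 rate. This stands, and is why lower healed shares are shown and why 30% vs 10% is only an illustration.

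**The Wound-QoL can still be answered after healing.** A reader might infer that a healed subject has nothing to rate at F1. Appendix G offers *not at all*, item 9 covers fear of new wounds and item 17 financial burden. A healed subject can answer these, so no gap in the instrument is claimed.

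**Conclusion.** The point holds in a limited form. Following 3.1, 4.4 and 5.21, the T4 quality-of-life score is not required of a subject healed at T1–T3, and its absence depends on the outcome. The consequence is confined to a T4 comparison and the T4 point of the repeated measures model. Such an estimate describes only subjects unhealed by T3, understates each arm's mean gain by p × g, and loses (pA − pB) × g of the arm difference when early healing differs.

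Under the assumed 30% vs 10% healed and g = 0.5–1.0 SD, the lost difference is 0.10–0.20 SD. With equal healing the arm contrast is not shifted and the cost between arms is precision only, a 12% larger SE at 20% healed per arm. That healed subjects have better quality of life is plausible but not shown in the documents.

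A reader might also infer bias in favour of the slower-healing arm. The calculation does not show that: among attenders the healing-mediated difference goes to zero and does not change sign.

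This is one visit of a secondary endpoint in an exploratory pilot without a power calculation. Severity is low; it is worth fixing because the fix is cheap and the data cannot be recovered.

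**What to change.** 1. State one quality-of-life schedule and use it in 3.2.2, 5.7 and Table 1.
2. In that schedule, collect the EQ-5D-5L and Wound-QoL at calendar week 4 (±2 days) from every randomised subject, healed or not. Preferably do this in clinic; otherwise use a posted paper form, because the EQ VAS is a scale that the subject marks and a telephone call cannot reproduce it. Record the mode of completion.
3. In Section 7, include all randomised subjects with a week-4 score in any T4 analysis, whatever their healing status.
4. Let healed subjects complete the Wound-QoL themselves, and do not impose scores: a fixed *not at all* could overwrite real answers, for example to items 9 and 17. Treat the EQ-5D-5L as the supporting analysis.

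The cost is some wording and a few extra questionnaires. Subjects are already enrolled for eight weeks under 8.5.1. The downside is that some forms would be completed remotely, mainly by healed subjects, so mode would be partly tied to outcome; this is why clinic completion is preferred and mode is recorded. No treatment or dressing rule changes.

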4.1 Overview

Subjects for the study will be recruited from the University of Miami (UM) patient population as well as other patients referred to UM for the study. The recruitment goal for this pilot study is 30 subjects. Considering up to 15% drop out rate, the study will enroll up to 35 subjects with the goal of having 15 subjects in each arm complete the study.

4.2 Criteria for inclusion

Criteria for inclusion in the study:

1. Adults, 18 years old and older (i.e. age \geq 18 years).
2. Venous leg ulcer (VLU) is present on the leg. VLU shall be full thickness but without exposure of deeper tissues (muscle bone or tendon).
3. If more than one ulcer is present, the largest ulcer meeting criteria shall be designated the study ulcer.
4. If more than one ulcer on the study ulcer limb, study ulcer shall be at least one centimeter from other ulcers.
5. Confirmed venous insufficiency, as documented up to 30 days prior to enrollment (Baseline Day 0), by either: a) Duplex ultrasonography, or b) Principal Investigator (PI) clinical assessment to include clinical signs and symptoms of venous ulcerations (e.g., hyperpigmentation of surrounding skin, varicosities, and/or lipodermatosclerosis).
6. Ankle-Brachial Pressure Index (ABI) exam with value of ≥ 0.80 in the affected limb
7. VLU has been treated with silver based therapy for at least 2 weeks within the previous 6 months.
8. VLU present for at least one month prior to screening visit 1.
9. VLU at least 1 cm in size but not larger than 100 cm².
10. After debridement, study ulcer demonstrates a clean wound bed.
11. If subject is a female of childbearing potential, subject must use at least one method of contraception acceptable by PI such as birth control pills, IUD, condoms, or sexual abstinence. At visit 1 urine pregnancy test must be negative.
12. Subject is able to comprehend all study related procedures and adhere to study schedule.
13. Subject is able to provide written informed consent.

4.3 Criteria for exclusion

Criteria for exclusion from the study:

1. Based on investigator medical judgment, ulcer is caused by any etiology exclusive of venous insufficiency.
2. Study Ulcer surface area (post-debridement) has increased or decreased by more than 30% in the period between screening visit 1 and treatment visit 1.

3. Study Ulcer exhibits clinical signs and symptoms of infection in the period between screening visit 1 and treatment visit 1 requiring oral antibacterial therapy.
4. Subject has known allergy to any of the materials used in the study.
5. Subject is unable to tolerate multi-layer compression therapy.
6. Based on investigator medical judgment, the Study Ulcer is suspicious for cancer (e.g. basal cell carcinoma or squamous cell carcinoma).
7. In the month prior to screening visit 1 subject was treated with systemic immunosuppressive medications for more than 2 weeks (e.g. chemotherapy, corticosteroids), and/or it is anticipated subject will require such medications during study period.
8. In the month prior to screening visit 1 subject was enrolled in any other research protocol for treatment of Study Ulcer.
9. The Subject has been diagnosed with malignant disease not in remission over the 5 years immediately preceding screening visit 1. (Except: cervical carcinoma in situ, cutaneous squamous cell carcinoma, cutaneous basal cell carcinoma that have been treated and have no evidence of recurrence or metastases).
10. Study ulcer area has been treated with radiation therapy at any time.
11. In the opinion of PI the subject has a medical condition such as autoimmune, renal, hepatic or hematologic disease that makes the subject an inappropriate candidate for participation in study.
12. In the month preceding screening visit 1 Study Ulcer has been treated with advanced tissue engineered devices matrix based devices (e.g., Apligraf™, Dermagraft™, Oasis™).
13. Subject is diagnosed with New York Heart Association Class III and IV congestive heart.
14. Failure: Class III: Symptoms with moderate exertion or, Class IV: Symptoms at rest.
15. Subject is diagnosed with diabetes mellitus that is poorly controlled and shall be defined as hemoglobin A1C >10%.
16. Study Ulcer is completely or more than 50% of the Study Ulcer is located on the foot (i.e. below the malleolus).
17. Subject is a female of childbearing potential, and refusing to use at least one method of contraception acceptable by PI such as birth control pills, IUD, condoms, or sexual abstinence.
18. Positive pregnancy test in screening visit 1 in a female of childbearing potential or active pregnancy or breast-feeding.
19. In the opinion of the PI the subject is unable to understand or comply with study related protocol including but not limited to providing informed consent.

4.4 Definition of study completion

A subject will be considered as completed the study if:

1. Subject healed during the treatment or follow up phase and completed all visits in the follow up phase.
2. Subject did not heal and completed all visits in the treatment and follow up phase.
3. Subject healed and then wound recurred and completed the follow up phase.

4.5 Subject withdrawal

A subject randomized into a treatment arm that has not completed the study as defined by section 4.4 will be considered incomplete.

Any subject is free to withdraw from the study without explanation and without future consequence on future care. Investigator will make every effort to obtain reason for withdrawal of subject especially eliciting any adverse event.

The PI may suspend or terminate a subject from the trial if deemed medically necessary. The reasons for suspension or termination will be recorded in the patient's study documents.

5. Study procedures

5.1 Subject identification:

After signing informed consent the subject will be assigned a subject ID number beginning with BSN2018001, BSN2018002 and so on. All study related materials (e.g. source documents, investigational device etc.) will be labeled with the subject ID a priori.

5.2 Randomization and sequence allocation:

A random sequence of numbers from 1-16 will be generated in two columns (A= Cutimed® Sorbact® and B= Acticoat®) in Excel (Microsoft, Redmond, WA). 8 envelopes with a card labeled Cutimed® Sorbact® and 8 with a card labeled Acticoat® will be created, sealed and assigned the random numbers a priori before randomization of the first subject BSN2018001 by two people who are not part of the research team. Envelopes will be placed in secure location in number order. This procedure will generate a random sequence of 16 subjects and 8 subjects in each arm. This procedure will be repeated for another block of subjects 17-30, and 31-36. The block of 31-36 will only be used if the total randomization does not reach to n=30. Once a subject is randomized, the investigator will open the next envelope in the sequence and write the subject number on the card and include it as part of the record in the source documents. This will be the treatment assignment for the rest of the study.

5.3 Blinding:

Due to the nature of the study and products, investigator blinding is unrealistic and subject blinding is unlikely. Research staff will avoid naming the dressing or suggesting the assignment to the subjects. However, an independent monitor with experience in treating wounds will be blinded to the treatment assignment and will confirm healing outcomes based on images. [name] and laboratory personnel will be blinded to the treatment assignments as well. Unblinding will occur when the study is officially closed for statistical analysis at <https://clinicaltrials.gov/>.

